# Laboratory assessments

Laboratory assessments will be the same for all time points and will include:

- 1. VerifyNow PRU assay
- 2. Whole blood vasodilator-stimulated phosphoprotein (VASP)
- 3. Light transmittance aggregometry (LTA)
- 4. Serum thromboxane B2
- 5. Total Thrombus-Formation Analysis System (T-TAS)

*Blood sampling*: Peripheral venous blood samples (10 mL) will be drawn through a short venous catheter inserted into a forearm vein and collected in anticoagulated and serum tubes at each study time point for all PD assessments. The first 2-4 mL of blood will be discarded to avoid spontaneous platelet activation.

#### Description of laboratory assays

*1) VerifyNow PRU assay:* The VerifyNow System is a turbidimetric based optical detection system which measures platelet induced aggregation as an increase in light transmittance (Accriva, San Diego, CA) and will be utilized according to manufacturer's instructions [15]. The assay is based on microbead agglutination and uses specific reagents for the pathways of interest. The instrument measures this change in optical signal and reports results in P2Y12 Reaction Units (PRU).

2) Whole blood vasodilator-stimulated phosphoprotein (VASP): VASP phosphorylation (VASP-P) is a marker of P2Y12 receptor signaling. VASP will be assessed the ELISA VASP-P kit (Biocytex Inc., Marseille, France) as previously described [15]. After a first step of parallel whole blood sample activation with PGE1 and PGE1+ADP, platelets from the sample are lysed, allowing released VASP to be captured by an anti-human VASP antibody, which is coated in the microtiter plate. Then, a peroxidase-coupled anti-human VASP-P antibody binds to phosphorylated serine 239 antigenic determinant of VASP. The bound enzyme peroxidase is then revealed by its activity on TMB substrate over a predetermined time. After stopping the reaction, absorbance at 450 nm is directly related to the concentration of VASP-P contained in the sample.PGE1 increases VASP-P levels by stimulation of adenylate cyclase. Binding of ADP

to P2Y12 leads to Gi-coupled inhibition of adenylate cyclase. Therefore, the addition of ADP to PGE1-stimulated platelets reduces PGE1-induced VASP-P levels. If P2Y12 receptors are successfully inhibited, addition of ADP will not reduce the PGE1-stimulated VASP-P levels. The platelet reactivity index (PRI) will be calculated after measuring VASP-P levels.

3) Light transmittance aggregometry (LTA): Platelet aggregation will be performed using LTA according to standard protocols. Blood will be collected in citrated (3.8%) tubes. LTA will be assessed using platelet rich plasma (PRP) by the turbidimetric method in a 2-channel aggregometer (Chrono-Log 490 Model, Chrono-Log Corp., Havertown) as previously described [15]. Platelet agonists will include ADP (20 µM), arachidonic acid (1 mM), collagen (3µg/ml), TRAP (15  $\mu$ M), and a combination of 2  $\mu$ g/ml collagen-related peptide + 5  $\mu$ M ADP + 15  $\mu$ M TRAP (CAT). The reagent cocktail CAT will allow to assess the overall platelet response to a combination of agonists that leads to activation of multiple platelet pathways (platelet-mediated global thrombogenicity). PRP will be obtained as a supernatant after centrifugation of citrated blood at 1000 rpm for 10 minutes. The isolated PRP will be kept at 37° C before use. Platelet poor plasma (PPP) will be obtained by a second centrifugation of the blood fraction at 2800 rpm for 10 minutes. Light transmission will be adjusted to 0% with the PRP and to 100% for the PPP for each measurement. Curves will be recorded for 6 minutes and platelet aggregation will be determined as the maximal percent change (MPA%) in light transmittance from baseline using PPP as a reference.

4) *Serum thromboxane B2*: The concentration of serum thromboxane B2 (TXB2) will be measured by using the TXB2 EIA kit (Cayman Chemical Company, Ann Arbor, MI), as previously described [15]. Briefly, samples will be diluted with EIA buffer to bring their concentrations within the range of the standard curve. A standard curve will be established by

NCT04484259

serial dilution of TXB2 between 1000 pg/mL and 7.8 pg/mL using EIA buffer as the matrix. The concentration of TXB2 in the samples will be calculated from a logistic 4-parameter fit of the standard concentrations versus percentage bound/maximum bound.

5) T-TAS: T-TAS is an automated microchip flow chamber system for the quantitative analysis of the thrombus formation process under blood flow conditions. T-TAS allows measurement of thrombus formation using the PL-chip (Diapharma, West Chester Township, OH) [18]. The PL-chip contains 25 capillary channels (width 40  $\mu$ m, depth 40  $\mu$ m) coated with type I collagen and is specifically designed for quantitative analysis of platelet thrombus formation, including platelet adhesion and aggregation, granule secretion, and thrombus growth in the absence of coagulation and fibrinolysis systems. In measurements using the PL-chip, a blood sample collected in a hirudin containing blood sampling tube. The platelet aggregates gradually increase in size and, in the process, occlude the capillary, resulting in an increase in flow pressure. In the present study, total platelet-derived thrombogenicity is expressed as the area under the flow pressure curve for the first 10 min for the PL-chip tested at a flow rate of 18  $\mu$ L/min (PL18-AUC10). Low PL18-AUC10 reflect reduced thrombus growth and rapid breakdown of the thrombus.

## Study endpoints, sample size calculation and statistical analysis

The primary end-point of the study is the comparison of the PRU determined by VerifyNow PRU between between aspirin plus ticagrelor 60 mg and ticagrelor 60 mg monotherapy at  $10 \pm 3$  days (trough effect). We hypothesize that ticagrelor monotherapy will be non-inferior to aspirin plus ticagrelor. Under the assumption of 0 difference in mean PRU between the 2 groups and a common standard deviation of 55 PRU, a sample size of 25 patients per group will allow for the 95% confidence interval (CI) to stay within 45 PRU with a 80% power and alpha=0.025. Considering ~15% of invalid samples due to haemolysis, technical issues or drop out, and the 3 arms of treatment a total of 87 patients will need to be included. Non-inferiority will be assessed using a 95% CI of the difference in mean PRU between the 2 strategies. The sample size has been calculated according to data previously published [19]. A PRU of 45 was arbitrarily chosen for the noninferiority margin for the upper 95% CI limit of the difference in line with prior similar investigations [20-22]. Secondary end points will include 1) the comparisons of platelet reactivity, measured by the different assays and agonists (see Description of laboratory assays for details) between the different randomized treatments; 2) the comparisons between ticagrelor 90 mg monotherapy and the randomized treatments; 3) the comparisons between groups of rates of high on-treatment platelet reactivity, defined according to consensus definitions [23]. Continuous variables will be expressed as a mean  $\pm$  SD or median [IQR]. Categorical variables will be expressed as frequencies and percentages. An analysis of variance method with a general linear model, with treatment as the main effect will be used to evaluate the primary non-inferiority endpoint as well as all superiority between-group comparisons at each time point. Least squares mean (LSM) differences in PRU between groups and the corresponding 2-sided 95% CI for the difference will be obtained based on the analysis of variance model and used to assess non-inferiority. Chi-square test and McNemar test will be used to compare categorical variables between groups. Statistical analysis will be performed using a SPSSv24.0 software (SPSS Inc. Chicago, IL).

The PD population will include all patients with PD data and without a major protocol deviation thought to affect significantly the PD of ticagrelor or clopidogrel. The PD population will be used for analysis of all primary and secondary PD variables. Erroneously treated patients

(eg, those randomized to one treatment but actually given the other) will be accounted for based on the actual treatment received.

All patients who will receive at least 1 dose of study drug will be included in the safety population. Safety will be evaluated by assessment of adverse events (including bleeding and ischemic). Adverse events will collected up to completion of the study. Bleeding events will be classified according to BARC (Bleeding Academic Research Consortium) criteria [24]. Stent thrombosis will be classified according to ARC (Academic Research Consortium) definitions [25]. MI, including peri-procedural MI, will be defined according to the universal definition [26]. Ischemic stroke will be defined as an ischemic cerebral infarction caused by an embolic or thrombotic occlusion of a major intracranial artery. Death will be considered cardiac in origin unless obvious non-cardiac causes can be identified.

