# 5. Research Plan:

#### **Research Design**

This will be a prospective, randomized, open-label study conducted in patients with CAD and diagnosis of DM. Patients can be on any background antiplatelet therapy, including aspirin or any P2Y12 inhibitor (clopidogrel, ticagrelor or prasugrel). The study will be performed at the Division of Cardiology of University of Florida Health, Jacksonville, Florida and patients will be recruited within the Cardiovascular services of our Institution. Patients will be screened by Cardiology Research staff, who will verify that all candidates meet inclusion and exclusion criteria. Results from blood tests performed within the last 90 days will be considered valid for screening purposes. If these are not available, a blood sample will be collected for the screening phase after the patient has signed informed consent.

Eligible patients will enter a 7-10 day run-in phase with aspirin 81 mg/ qd plus ticagrelor 90 mg bid after which they will discontinue aspirin and maintain ticagrelor 90 mg bid monotherapy for  $10\pm 3$  days. After this period, patients will be randomized using a randomly generated computer sequence in a 1:1:1 fashion to one of three treatment groups: a) ticagrelor 60 mg bid monotherapy; b) aspirin 81 mg qd plus ticagrelor 60 mg bid; c) aspirin 81 mg qd plus clopidogrel 75 mg qd. Randomized treatment will be maintained for  $10\pm 3$  days. The approach of having a run-in phase with aspirin plus ticagrelor 90 mg followed by ticagrelor 90 mg monotherapy is in line with the TWILIGHT trial to assess for tolerability and compliance with ticagrelor therapy [6, 17]. The approach of having an aspirin plus ticagrelor 60 mg regimen as well as an aspirin plus clopidogrel regimen is reflective of guideline recommendations for long-term secondary prevention [1,16]. The current investigation will test the hypothesis that the experimental strategy of ticagrelor 60 mg monotherapy will not result in significant changes in P2Y12 inhibitory effects compared with aspirin plus ticagrelor 60 mg and will provide more effective platelet inhibition compared with aspirin plus clopidogrel. The study design is illustrated in Figure 1 and a further breakdown of what will occur during the course of the study:

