#### 6. Possible Discomforts and Risk:

In clinical trials, the most important adverse effect associated with the use of ticagrelor was bleeding. The risk of major bleeding with ticagrelor 90 and 60 mg was 2.8% and 2.3%, respectively; the combined risk of intracranial hemorrhage or fatal bleeding was <1% [7,27]. However, such bleeding prevalence occurred in the setting of long-term trial (median follow-up of 9 and 33 months in PLATO and PEGASUS) with bleeding events that accrued over time, while our study is limited to only  $30 \pm 3$  days of therapy. Ticagrelor will be compared with clopidogrel, which is also associated with an increased risk of bleeding compared with placebo [28]. We do not anticipate that ticagrelor will significantly increase the risk of bleeding compared with clopidogrel. Dyspnea has been reported as the main non-bleeding side effect with ticagrelor and occurs in up to 15.8% of patients [7,27]. Below is a complete lists of potential medication risks:

- Bleeding
- Dyspnea (shortness of breath)
- Headache
- Cough
- Mild to moderate diarrhea
- Nausea
- Hypotension (low blood pressure)
- Hypertension
- Dizziness
- Non-cardiac chest pain
- Back Pain
- Fatigue
- Cardiac (heart) chest pain

Patients who discontinue ticagrelor therapy will be switched back to their standard of care treatment regimen.

All clinical events described above, if they were to occur, as well as death, myocardial infarction, stroke, and urgent revascularization procedure with PCI or coronary artery bypass grafting will be recorded. All serious adverse events will be submitted to the AstraZeneca Product Safety mailbox. Bleeding data will be collected using BARC definitions [24]. The study will have a DSMB, comprised of 2 faculty members (2 cardiologists), not directly involved in

the research. In the event of a report of a serious adverse event the local committee will meet and antiplatelet treatment management will be managed according to physician recommendation.

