## 9. Publication Strategy/Additional Information:

Study subjects will be identified first (months 1-21): we expect to enroll approximately 3 subjects monthly and complete enrollment in 21 months (total: 87 subjects enrolled). Months 22-24 will be implied for completion of follow-up, statistical analysis and abstract or manuscript preparation. We intend to present data at a major scientific meeting at completion of the study. We anticipate no major problems with the described protocol since the approach is a straightforward prospective study and is based on well-established methods.

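### The total of 87 does not follow from 25 evaluable per group with about 15% loss (that gives 90), and the plan does not say whether the allowance covers the run-in; the inflation slip alone leaves power at 80%

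*Combined protocol and SAP*

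**What the plan says.** The sample size paragraph (Section 5, Study endpoints, sample size calculation and statistical analysis) supposes that the two ticagrelor groups truly do not differ and that the SD is 55 PRU in each. Its key statement is: "a sample size of 25 patients per group will allow for the 95% confidence interval (CI) to stay within 45 PRU". The target power is 80%, and the alpha given is 0.025.

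The margin is applied on one side, as the "noninferiority margin for the upper 95% CI limit of the difference". The paragraph then allows roughly 15% for samples spoiled by haemolysis or technical problems and for drop-out, takes the three arms into account, and states that "a total of 87 patients will need to be included". No inflation formula is shown.

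Section 9 repeats the total as a recruitment target: "complete enrollment in 21 months (total: 87 subjects enrolled".

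Under Research Design, enrolment and randomisation are separate events: "Eligible patients will enter a 7-10 day run-in phase". In that phase they take aspirin and ticagrelor 90 mg together, then ticagrelor 90 mg alone for 10 ± 3 days, and only then are they randomised 1:1:1. The stated purpose of this phase is to check tolerability and compliance. No run-in loss rate is given.

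**The concern.** There are two separate questions.

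The first is arithmetic. To keep 25 patients after losing a fraction d, one divides by 1 − d. Multiplying by 1 + d always falls short, because the loss applies to the inflated number and not to the 25. The stated 87 is what multiplication gives.

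The second is the point of counting. Power depends on patients who are randomised and have a valid trough PRU. Section 9 counts the 87 as enrolled, which is before the run-in. The sample size paragraph says only that they are included, and it does not say whether its drop-out component starts at enrolment or at randomisation.

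At stake is the headline sample size for a non-inferiority primary endpoint: whether it yields the evaluable number behind the power statement, and whether a reader can tell how many patients must be randomised.

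**Working it through.** **Inputs.** From the sample size paragraph: true difference 0, SD 55 PRU, margin 45 PRU, one-sided alpha 0.025, power 80%, 25 evaluable per group, loss of about 15%, three arms. From Research Design: 1:1:1 allocation after the run-in. From Section 9: 87 counted at enrolment.

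**Step 1. Reproduce the 25 per group.** The normal approximation is n = 2 × [55 × (1.960 + 0.842)/45]² = 23.45, rounded up to 24. The non-central t calculation uses non-centrality 45/(55 × √(2/n)):

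- With 2n − 2 degrees of freedom (two-sample t), power is 79.2% at n = 24 and 80.9% at n = 25.
- With the 3n − 3 degrees of freedom of the planned three-arm ANOVA, power is 79.8% at n = 24 and 81.4% at n = 25.

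On either basis 25 is the smallest n that reaches 80%. The plan's 25 is correct.

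**Step 2. Reproduce the 87.**

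- Multiplying: 25 × 1.15 = 28.75, rounded up to 29; 29 × 3 = 87. This matches the plan.
- Dividing: 25/0.85 = 29.41, rounded up to 30; 30 × 3 = 90.
- Dividing the total without equal arms: 75/0.85 = 88.24, rounded up to 89.

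Multiplication gives exactly 87; division gives 89 or 90.

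**Step 3. What 87 delivers if 15% covers all loss.**

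- Evaluable per arm: 87 × 0.85/3 = 24.65, which is 0.35 short of 25.
- Power at 24.65: 80.3% (two-sample t) or 80.9% (three-arm degrees of freedom).
- Loss at which 87 still leaves 25 per arm: (29 − 25)/29 = 13.8%.

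**Step 4. What 87 delivers if run-in loss is additional.** The run-in lasts from 7 + 7 = 14 to 10 + 13 = 23 days. If a fraction r of those enrolled leaves before randomisation and 15% of the remainder is then lost, evaluable per arm = 87 × (1 − r) × 0.85/3. The values of r below are assumptions.

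| Run-in loss r (assumed) | Evaluable per arm | Power, two-sample t | Power, three-arm df |
|---|---|---|---|
| 0% | 24.65 | 80.3% | 80.9% |
| 1% | 24.4 | 79.9% | 80.5% |
| 5% | 23.4 | 78.2% | 78.8% |
| 10% | 22.2 | 75.9% | 76.5% |
| 15% | 21.0 | 73.4% | 74.1% |

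On the two-sample t basis a 1% run-in loss already takes power just under 80%. With three-arm degrees of freedom power is 80.1% at r = 2% and 79.7% at r = 3%. The slack is thin on both.

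**The case against.** The strongest reply is that the plan promises 80% power and, on its own allowance, still has it. At exactly 15% loss power is 80.3%, or 80.9% with the degrees of freedom of the planned analysis. The allowance is given as approximate, and 13.8% is a fair reading of about 15%. Without rounding each arm up, the gap is two patients. The plan shows no formula, so multiplication by 1.15 is inferred from the match and not stated. All of this stands, and it limits the inflation slip to a small correction.

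On the run-in, the allowance names drop-out without confining it to the period after randomisation, and Section 9 counts from enrolment. Read together, the 15% could cover every loss from enrolment on. In that case Step 3 applies and power stays above 80%. This also stands, so the lower rows of the table are conditional.

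Two stronger readings are tempting, and the documents support neither. A reader might infer that the inflation slip by itself makes the trial underpowered; Step 3 shows that it does not. A reader might also take the dyspnoea figure in Section 6 ("occurs in up to 15.8% of patients") as a likely run-in loss. It is the frequency of a side effect, not of stopping treatment. That section gives the trials in question median follow-up of 9 and 33 months, against a run-in of 14–23 days, and patients here may already be taking ticagrelor at entry. The figure gives no discontinuation rate for this run-in and is not used above.

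The reply does not show that 87 follows from 25 and 15%, nor does it tell a reader which count or which losses are meant.

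**Conclusion.** Wrong as written, but minor. The total in the sample size paragraph and in Section 9 does not follow from the plan's own inputs, which give 90 with equal arms (89 without). The cost of the slip is 0.35 evaluable patients per arm and about 0.5 to 0.6 percentage points of power (80.9% to 80.3%, or 81.4% to 80.9%). The stated 80% holds.

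The counting point is an ambiguity and not a demonstrated shortfall. It becomes material only if the allowance excludes run-in loss. Power would then be about 73% to 78% for assumed run-in losses of 15% down to 5% (two-sample t). That range rests on assumed rates, on the plan's SD of 55 PRU and on a true difference of zero.

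**What to change.** 1. Restate the total in both the sample size paragraph and Section 9. Either give 25/(1 − 0.15), so 30 per arm and 90 in all, or keep 87 and state that it tolerates 13.8% loss and yields 24.65 evaluable per arm at 15%.
2. State whether the total counts patients enrolled or patients randomised, and use the same term in both places.
3. State whether the 15% includes loss during the run-in. If it does not, give the expected run-in loss and restate the evaluable number and power, or the enrolment needed. For example, randomising 90 would take 90/0.95 = 95 enrolled at 5% run-in loss, 90/0.90 = 100 at 10%, and 90/0.85 = 106 at 15% (rounded up, rates assumed).

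Keeping 87 costs only wording, with a slightly less favourable tolerated loss on record. Moving to 90 costs three patients. Enrolment beyond that is needed only if run-in loss proves to be additional and the sponsor wants to hold 30 randomised per arm.

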## Figure 1. OPTIMUS-7 study design.

- Potential subjects will first be screened by research personnel to see if they are eligible for the study. Results from blood tests performed within the last 90 days which they would have performed as part of their standard of care will be considered valid for screening purposes.
- If the potential subject is a woman of childbearing potential, a pregnancy test will be done. If subject is found to be pregnant, the participation in this study will end.
- If subject is eligible for the study based on the screening results, the subject will start the study procedures as outlined below:
  - Every participant will start a so called run-in phase during and will be treated with aspirin 81mg once a day, and Ticagrelor 90mg twice a day for 7-10 days. After that, the participant will stop taking the aspirin and only take the Ticagrelor 90mg for 10±3 days. This run-in phase is to make sure that subjects are able to take the medication without side effects.

- After completing the run-in part of the study, subjects will be randomized to one of three medication groups and take study medication for 10 ± 3 days:
  - a) Ticagrelor 60mg twice daily (without aspirin)
  - b) Ticagrelor 60mg twice daily, plus aspirin 81mg once daily
  - c) Clopidogrel 75mg once daily, plus aspirin 81mg once daily

Blood sampling for PD testing will be performed at 4 time points: a) after completing 1week aspirin plus ticagrelor 90 mg run-in phase; b) after completing  $10\pm3$  days of treatment with ticagrelor 90 mg monotherapy; c) after completing  $10\pm3$  days of randomized treatment. At each time point PD assessments will be performed  $12 \pm 2$  hours after last ticagrelor dose and 24 hours after last clopidogrel dose in order to define trough levels of platelet inhibition. At the last time point (after  $10\pm3$  days of randomized treatment) blood samples will also be collected 2 hours after administration of the antiplatelet regimen in order to assess for peak levels of platelet inhibition. The Ticagrelor (Brilinta) tablets are being provided by AstraZeneca. The Clopidogrel and aspirin will be provided by the Cardiovascular Research Department. All medications will dispensed by the Cardiovascular Research Department and will be packaged using supplies and guidelines provided by UF Health Research Pharmacy.

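### Does the lack of a named paired method for ticagrelor 90 mg monotherapy versus the randomised treatments leave secondary endpoint 2 without a valid analysis?

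*Combined protocol and SAP*

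**What the plan says.** Research Design puts all eligible patients on aspirin plus ticagrelor 90 mg, "after which they will discontinue aspirin and maintain ticagrelor 90 mg bid monotherapy for" 10±3 days, and only then randomises them 1:1:1 to three regimens, none of which contains 90 mg. The text under Figure 1 confirms that this applies to all ("Every participant will start a so called run-in phase"). It schedules one blood sample after 10±3 "days of treatment with ticagrelor 90 mg monotherapy; c) after completing" the randomised period. These samples are taken at trough. A peak sample is added only at the last visit, where "blood samples will also be collected 2 hours after administration of the antiplatelet regimen".

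The section on study endpoints, sample size calculation and statistical analysis lists "the comparisons between ticagrelor 90 mg monotherapy and the randomized treatments" as secondary endpoint 2, and "the comparisons between groups of rates of high on-treatment platelet reactivity" as secondary endpoint 3. For continuous data it names an analysis of variance within a general linear model, with treatment as main effect. This serves the primary endpoint and "all superiority between-group comparisons at each time point". For categorical data it says: "Chi-square test and McNemar test will be used to compare categorical variables between groups". No paired t-test, signed-rank test, mixed model or patient effect is named anywhere.

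**The concern.** Endpoint 2 crosses visits. The 90 mg values and the randomised-treatment values come from the same people, and at no time point are some patients on 90 mg monotherapy while others are on a randomised regimen. A model confined to between-group comparisons at each time point therefore cannot produce endpoint 2 as worded. McNemar's test needs pairs, yet the sentence naming it speaks of groups, and the one categorical platelet endpoint listed is also worded as between groups. On a literal reading, the endpoint has no method and the paired test has no endpoint.

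The endpoint matters to readers. In the monotherapy arm it is the trial's only view of 90 mg against 60 mg with aspirin absent at both visits. If an analyst stretched the analysis of variance by treating 90 mg as one more independent group, the within-patient correlation would be ignored. With positive correlation, the intervals would be wider than they need to be.

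**Working it through.** **Inputs.** From the statistical section: SD 55 PRU, 25 evaluable patients per group, margin 45 PRU, one-sided alpha 0.025, power 80%, about 15% loss, 87 in total. Not in the documents, so assumed: within-patient correlation ρ of 0, 0.3, 0.5 or 0.7, and SD 55 at the 90 mg visit as well.

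**1. The plan's own figure.** n per group = 2 × 55² × (1.960 + 0.842)² / 45² = 23.4, rounded up to 24 by the normal formula. With the noncentral t, power is 79.2% at 24 and 80.9% at 25, so 25 is right. Then 25 × 1.15 = 28.75, rounded up to 29, and 29 × 3 = 87. None of this uses the 90 mg visit. The primary endpoint compares two arms at one time point, which the named model handles.

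**2. The misuse that could occur.** All patients contribute a 90 mg value, so entering 90 mg as a fourth group gives about 3 × 25 = 75 values against 25 per arm.

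- SE as the model would report it: 55 × √(1/25 + 1/75) = 12.70 PRU.
- The two means share 25 patients, so their covariance is ρ × 55²/75. Correct SE of the same difference: 55 × √(1/25 + 1/75 − 2ρ/75).
- Error degrees of freedom: 150 − 4 = 146, t = 1.976. Reported 95% half-width: 1.976 × 12.70 = 25.1 PRU.

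**3. The sensible analysis.** Within-arm paired t: SE = 55 × √(2(1 − ρ)/25), half-width = 2.064 × SE (24 degrees of freedom).

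| ρ (assumed) | Four-group SE, reported | Correct SE of that difference | Overstatement | Four-group half-width, reported | Paired half-width |
|---|---|---|---|---|---|
| 0 | 12.70 | 12.70 | 1.00 | 25.1 | 32.1 |
| 0.3 | 12.70 | 11.71 | 1.08 | 25.1 | 26.9 |
| 0.5 | 12.70 | 11.00 | 1.15 | 25.1 | 22.7 |
| 0.7 | 12.70 | 10.24 | 1.24 | 25.1 | 17.6 |

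The paired interval at ρ = 0 has half-width 32.1, so the two are equal when 32.1 × √(1 − ρ) = 25.1, that is ρ = 1 − (25.1/32.1)² ≈ 0.39. Below that, the simple paired interval is the wider one, because it uses 25 values of 90 mg rather than 75.

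**4. A worse misuse.** Comparing each arm's 25 values with its own 25 earlier values by a two-sample t-test gives SE 55 × √(2/25) = 15.56 and half-width 2.011 × 15.56 = 31.3. The overstatement is 1/√(1 − ρ) = 1.00, 1.20, 1.41 and 1.83. In simulation, the true size of the nominal 5% test falls to about 5.0%, 2.0%, 0.7% and 0.1%. The plan names no such test.

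**5. The wording.** The arms are parallel and contain different patients, so McNemar's test cannot be run across them. The only categorical comparison in this design that it fits is a patient's change between visits. The sentence therefore reads as two tests listed together: chi-square between arms, McNemar within patients.

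**The case for a change.** The best case for a change is that one sentence would settle the matter before data are seen, at no cost: both trough samples are already scheduled, so no patient, visit or blood draw is added. Without it, paired, pooled and mixed-model analyses all stay open, across five assays and several aggregometry agonists. Endpoint 2 will also be read with interest, because the trial is framed around 60 mg without aspirin. At ρ = 0.5 the two-sample t-test would have 47% power for an illustrative 30 PRU change, against 75% for the paired test.

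Part of this stands. The method for endpoint 2 is not named, and the McNemar sentence is loose. But those power figures belong to a 25-versus-25 test that the plan does not mention. The misuse closest to the stated model overstates the SE by at most a factor of 1.24 over the range examined, and its reported interval is narrower than the simple paired one below ρ of about 0.39. The gain in precision therefore depends on a correlation the documents do not give. The remaining freedom of method concerns a secondary endpoint with no stated power, margin or decision rule.

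**Conclusion.** No change to the plan follows. This is a gap that an analyst would fill sensibly, together with a slip of wording. The design makes the pairing obvious, the general linear model extends to repeated measures, and naming McNemar's test signals that within-patient comparisons were in mind. Trough to trough is the natural contrast, since the 90 mg visit has no peak sample.

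If the analysis of variance were nevertheless stretched to a fourth group, the SE would be too large by a factor of 1.00 to 1.24 for ρ from 0 to 0.7. The result would be wider intervals and no excess of false positives. This rests on a common SD of 55 PRU at both visits, 25 evaluable patients per arm and a correlation that is not negative. The primary non-inferiority comparison, the 25 per group and the total of 87 are the same whichever method is used for endpoint 2.

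### The primary model names treatment only; adding the pre-randomisation trough PRU as a prespecified covariate would probably tighten the non-inferiority interval at very small cost

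*Combined protocol and SAP*

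**What the plan says.** The primary endpoint, under Study endpoints, sample size calculation and statistical analysis, compares trough PRU after 10±3 days of randomised treatment between ticagrelor 60 mg alone and ticagrelor 60 mg with aspirin. The model is an analysis of variance "with a general linear model, with treatment as the main effect will be used to evaluate the primary non-inferiority endpoint". Its least squares mean difference and two-sided 95% CI decide non-inferiority against a margin of 45 PRU. No covariate is named anywhere in the document.

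The candidate covariate is already in the schedule:

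- **Research Design:** randomisation follows the ticagrelor 90 mg monotherapy period ("After this period, patients will be randomized using a randomly generated computer sequence in a 1:1:1 fashion to one of three treatment groups").
- **Blood sampling text under Figure 1:** one sampling point comes after 10±3 "days of treatment with ticagrelor 90 mg monotherapy". The trough timing is general ("At each time point PD assessments will be performed" 12±2 hours after the last ticagrelor dose).
- **Laboratory assessments:** "Laboratory assessments will be the same for all time points", and VerifyNow PRU is first on the list.

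The only planned use of that value is in the second secondary endpoint, "the comparisons between ticagrelor 90 mg monotherapy and the randomized treatments".

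**The concern.** A pre-randomisation measurement by the same assay, at the same trough timing and in the same patients, is usually the most useful covariate for a continuous outcome. Here it is collected but left out of the comparison that decides the trial.

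What is at stake is the width of the interval relative to the 45 PRU margin. The design sits close to its power target: after the plan's own 15% loss, 24 to 25 patients per arm remain. Randomisation protects the unadjusted estimate, so no bias is alleged.

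**Working it through.** **Inputs from the statistical section.** SD 55 PRU, margin 45 PRU, true difference 0, one-sided alpha 0.025 (the upper limit of a two-sided 95% CI), 80% power, 25 evaluable per arm, about 15% loss, 87 enrolled in three arms.

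**Assumption.** The correlation ρ between the pre-randomisation and final trough PRU within the ticagrelor arms is not in the documents. It is shown as a range from 0.

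**1. The plan's own figures.**
- Normal formula: n = 2 × (1.960 + 0.842)² × 55² / 45² = 23.4, so 24 per arm.
- With the t distribution at n = 25: SE = 55 × √(2/25) = 15.56, df = 48, noncentrality 45/15.56 = 2.89. Power is 80.9% and the 95% CI half-width is 2.011 × 15.56 = 31.3 PRU. At n = 24, power is 79.2%.
- Enrolment: 25 × 1.15 = 28.75, so 29 per arm and 29 × 3 = 87. The stated figures reproduce.
- Expected evaluable: 87 × 0.85 = 73.95, or 73.95/3 = 24.65 per arm.

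**2. ANCOVA in the two ticagrelor arms.** The residual SD is 55 × √(1 − ρ²). One more degree of freedom is spent (df = 2n − 3), and chance baseline imbalance inflates the variance:

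SE = 55 × √(1 − ρ²) × √[(2/n) × (1 + F/(2n − 2))], with F distributed as F(1, 2n − 2).

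Power is the noncentral-t power averaged over F. The mean inflation factor at n = 25 is 1 + 1/46. Example at ρ = 0.5: half-width = 2.012 × 55 × √0.75 × √0.08 × √(1 + 1/46) = 27.4 PRU.

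| Analysis (25 per arm) | Half-width, PRU | Power |
|---|---|---|
| Unadjusted | 31.3 | 80.9% |
| ANCOVA, ρ = 0 | 31.6 | 80.0% |
| ANCOVA, ρ = 0.2 | 31.0 | 81.6% |
| ANCOVA, ρ = 0.3 | 30.2 | 83.6% |
| ANCOVA, ρ = 0.5 | 27.4 | 89.9% |
| ANCOVA, ρ = 0.7 | 22.6 | 97.5% |

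Power equals the unadjusted value at ρ = 0.148. At ρ = 0.5 the gain is worth about 32 unadjusted patients per arm (89.6% at 32, 90.5% at 33). With 24 per arm and ρ = 0.5, power is 88.6% against 79.2% unadjusted. In simulation (20,000 runs per scenario), one-sided type I error was about 0.023 to 0.026 for both two-arm models.

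**3. Which arms are fitted.** If clopidogrel PRU is unrelated to the ticagrelor baseline (an assumption, with SD 55), simulation with 40,000 runs gives:

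| Fit | ρ = 0.5 | ρ = 0.7 |
|---|---|---|
| Three arms, common slope | 86.6% | 92.7% |
| Three arms, arm-specific slopes | 88.1% | 95.5% |
| Two ticagrelor arms (formula in step 2) | 89.9% | 97.5% |

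**4. Missing baselines.** Suppose 15% of pre-randomisation values are missing (an assumption).
- Dropping those patients leaves about 25 × 0.85 = 21 per arm. Power is then 83.8% at ρ = 0.5 but 76.3% at ρ = 0.3, which is below the unadjusted analysis of all 25.
- Imputing the overall baseline mean keeps about 88.4% power at ρ = 0.5, with one-sided type I error of about 2.5% (60,000 runs).

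**The case against.** The strongest reply is that this is a preference. The planned analysis is valid, agrees with its sample size and meets its power target, and no conclusion becomes wrong if the advice is ignored. That stands, and it limits the point to an optional improvement.

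The gain also rests on an unknown correlation. The baseline is taken on 90 mg and the outcome on 60 mg about ten days later, with aspirin restarted in one of the two arms. At ρ = 0.2 the benefit is only 0.7 points of power and 0.3 PRU. This stands too, and it is why the claim is no stronger than probable. In its favour, both arms stay on the same drug, and Background and Significance describes the two ticagrelor doses as giving similar platelet inhibition. A correlation above 0.15 is therefore plausible, though not shown.

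The plan may also intend one three-arm model with pooled error (df = 72). Unadjusted power would then be 81.4%, the two-arm ANCOVA would break even at ρ of about 0.19, and its worst-case cost would be 81.4 − 80.0 = 1.4 points. This is correct but small, and it does not change the direction.

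Finally, a general linear model can carry covariates, and the text does not say that treatment is the only term. But none is named, and in a non-inferiority test a covariate chosen after the data are seen would be open to challenge.

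**Conclusion.** The point holds as an optional gain in precision. The decisive model leaves out a baseline value that the trial already collects. Using it would probably narrow the interval: by 12% at ρ = 0.5 (31.3 to 27.4 PRU, with power up 9 points), and by very little below ρ of about 0.3. The downside is about 1 point of power if ρ is 0, or 1.4 points against a pooled three-arm ANOVA.

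These figures assume SD 55 in each arm, a linear relation between baseline and outcome, 25 evaluable per arm, and no loss of patients for a missing baseline. The enrolment figure ("a total of 87 patients will need to be included") is not put in question. Confidence is medium because ρ is not documented.

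**What to change.** Before outcome data are seen, write into the statistical section:

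- **Model.** ANCOVA of trough PRU at 10±3 days of randomised treatment, with treatment as factor and trough PRU at the end of ticagrelor 90 mg monotherapy as a continuous covariate, fitted in the two ticagrelor arms. Take the least squares mean difference and two-sided 95% CI from this model. If a single three-arm model is preferred, use arm-specific slopes with a centred covariate.
- **Missing baseline.** Impute the overall baseline mean, regardless of arm, so that every patient with a valid primary PRU stays in the analysis.
- **Sensitivity.** Keep the unadjusted ANOVA.
- **Secondary assays that respond to aspirin (thromboxane B2, arachidonic acid aggregometry).** If the same adjustment is extended to these, allow unequal slopes or leave them unadjusted, because the baseline is aspirin-free and two arms then restart aspirin.

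The cost is a few lines of text, one covariate in the planned SPSS model and one degree of freedom. No new samples, visits or patients are needed.
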